collected to support and validate the outcome of machine learning models. An analysis of first round data detected post-semester depression among freshmen with accuracy of ~86% and change in severity levels with accuracy of 78.6%. A machine learning pipeline was developed to process data on a sensor by sensor basis to identify the best set of sensors that provide the highest accuracy and the minimal set of features required for accurate inferences above the majority class baselines.

We adapted this data to adolescents and used their data to replicate the analysis, rederiving the algorithms.

We will use the data collected from the first phase to create an application, MoodRing, to provide feedback to adolescents, parents, and clinicians on symptom severity using passive sensing technology, to understand whether this application improves the quality of depression management through increasing the application of self-management activities and utilization of timely engagement with healthcare as well as exchange of passively monitored mood information between adolescents, parents, and providers.

Study Objectives

Evaluate the efficacy of MoodRing in a randomized trial.

PRIMARY: 1) Does MoodRing compared to usual care improve the self-management of depression (i.e. active involvement of adolescent patient in managing their depression)? AT 3 MONTHS

EXPLORATORY:

2) Does MoodRing compared to usual care improve the quality of depression management as measured by:

- a) depression symptom reassessment
- b) medication adherence in those on medication
- c) therapy adherence in those in therapy

3) Does MoodRing compared to usual care result in:

- a) less healthcare utilization
- b) decreased depressive symptoms
- c) improved sleep quality
- d) increased application of self-management activities

3) Is improvement in self-management of depression mediated by perceived severity, social support, self-management knowledge and skills, and self-efficacy?

4) Do healthcare providers, adolescents, parents report satisfaction with MoodRing?

Study Design & Methods

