Randomized trial. Study procedures: We will recruit adolescents with a history of depression using similar mechanisms as in the Phase 1 study (IRB protocol #18120176). This will include recruitment through clinical sites at CAYAH (4 clinical sites) and the University of Pittsburgh Research Registry, Pitt+Me, run by the Clinical and Translational Science Institute as well as from the STAR center. Most participants for the Phase 1 study were successfully recruited through the STAR center. We will also recruit using social media advertisements. The research assistant (RA) will screen interested adolescents for meeting inclusion/exclusion criteria – have a prior or present history of depression per self- report and/or clinician diagnosis - and enroll those with a score of at least 5 or higher on the PHQ-9 who do not have active suicidality. Most adolescents recruited from the STAR center will have completed their acute phase of treatment in intensive outpatient treatment and will be receiving outpatient psychotherapy and/or antidepressant management. Adolescents age 12-18 and their parent will be consented for the study and be sent an online survey for baseline measures. Those who complete the baseline measures will then be randomized to receive the MoodRing intervention or treatment as usual and asked to complete data collection at 3 months and 6 months by online survey. Additionally, data will be collected via the electronic health record and from patients' healthcare providers who consent to participate in the study. Randomization: Adolescents will be

randomized at a 1:1 ratio (using randomized block sizes) to MoodRing with feedback to adolescent, parent, and healthcare provider team or to usual care with collection of passive sensing and survey data without the use of the MoodRing app. The randomization tables will be generated by the study statistician.

Eligibility Criteria

Included if

- age 12 -18
- prior or present history of depression per self-report and/or clinician diagnosis
- scores between 5 or higher on PHQ-9 consistent with at least mild symptoms
- read and understand English
- has an Android or iOS smartphone compatible with AWARE APP and access to a smartphone data plan
- currently in United States

Excluded if

- currently actively suicidal (have suicidal thoughts and plan with an intent to act on it)

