- plans to travel to countries belonging to the European Union (Austria, Belgium, Bulgaria, Croatia, Cyprus, Czech Republic, Denmark, Estonia, Finland, France, Germany, Greece, Hungary, Ireland, Italy, Latvia, Lithuania, Luxembourg, Malta, The Netherlands, Poland, Portugal, Romania, Slovakia, Slovenia, Spain, Sweden), the

United Kingdom (England, Scotland, Wales, and Northern Ireland), Norway, Iceland, or Lichtenstein in the next 6 months for more than 2 weeks at a time

Parent/Guardian

Included if:

- adolescent qualifies for study and assents to enroll
- understands English
- currently in United States
- has a smartphone device that can download the intervention application

Excluded if:

- If their adolescent child is excluded

Statistical Considerations

The primary outcome is self-management using the Partners in Health Scale which is a continuous scale of self-management knowledge and behavior. <https://www.publish.csiro.au/PY/PY03022> Our planned sample would give us the power to detect a small effect size. For the full sample (N=200): 80% power (alpha=0.05) to detect cohens d = .40. Complete data with 10% dropout (N=180): 80% power (alpha=0.05) to detect cohens d = .42."

Data Analysis: Baseline summary statistics will be displayed. The CONSORT diagram will be completed to ensure reporting transparency. The main outcome for Phase II is self-management of depression. To assess intervention efficacy, the primary approach will be an intent to treat analysis with a mixed model with a random intercept treatment as the effect of interest. Predictors will be treatment, time, and treatment*time interaction. Covariates will be age, history of therapy, and phq9 total score.

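### The primary mixed model neither adjusts for baseline Partners in Health score nor constrains the arms to a common baseline mean, so it gives up precision for the 3-month effect

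*Combined protocol and SAP*

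**What the plan says.** Study Objectives puts the primary question at 3 months ("active involvement of adolescent patient in managing their depression)? AT 3 MONTHS"). Statistical Considerations names the outcome: "The primary outcome is self-management using the Partners in Health Scale which is a continuous scale of self-management knowledge and behavior".

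The Data Analysis paragraph describes an intention-to-treat "mixed model with a random intercept treatment as the effect of interest". It continues "Predictors will be treatment, time, and treatment*time interaction" and then "Covariates will be age, history of therapy, and phq9 total score". Nothing else in the document adds baseline PIH to the model or sets the arms equal at baseline.

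On timing, Study Design & Methods says "Those who complete the baseline measures will then be randomized to receive the MoodRing intervention or treatment as usual", and that participants are "asked to complete data collection at 3 months and 6 months by online survey". The instruments in the baseline survey are not listed.

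The power statement for completers reads "Complete data with 10% dropout (N=180): 80% power (alpha=0.05) to detect cohens d = .42".

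**The concern.** In a randomised trial with a continuous outcome, the baseline value of that outcome is usually among the strongest predictors of its later value. The listed covariates include a symptom score but not the self-management score itself. A treatment main effect with no constraint leaves the arm means free at every visit, so fitting a mixed model does not by itself recover the baseline information.

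The plan also leaves open three things that decide what is tested: whether baseline is an outcome row, whether time is categorical or linear, and which contrast answers the 3-month question. If baseline is a row and the reference time, the coefficient labelled treatment is only the arm difference at baseline, which randomisation makes zero in expectation.

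At stake is the precision of the only primary comparison, with about 180 participants expected to have follow-up data.

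**Working it through.** **1. The plan's own figures.** Two-sample t-test, two-sided 5%, SD 1. With 100 per arm and d = 0.40, power is 80.4%; with 90 per arm and d = 0.42, it is 80.0%. The detectable d at 80% power is 0.398 and 0.420. Both stated figures reproduce, as an unadjusted comparison of one follow-up score. Also, 200 × 0.9 = 180.

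**2. Inputs.**
- From the protocol: 1:1 allocation, 90 per arm after dropout, d = 0.42, surveys at baseline, 3 and 6 months, random intercept (equal correlation between visits).
- Assumed, because not given: correlation r between PIH scores of 0.3, 0.5 or 0.7; correlation p between PHQ-9 and PIH at each visit of 0 (PHQ-9 ignored), 0.2 or 0.4; equal variances; complete data at 90 per arm; PHQ-9 taken as a baseline value.

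**3. Variance of the 3-month effect,** relative to an unadjusted 3-month difference (2/n = 1 unit), ignoring PHQ-9:
- 3-month difference, with only months 3 and 6 as rows or with a baseline row and free arm means: 1.
- Change from baseline to month 3 (treatment by time): 2(1 − r).
- Baseline PIH as covariate, or common baseline mean: 1 − r².

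With PHQ-9 in the model, the residual variance is 1 − p² and the residual covariance is r − p². The 3-month difference then has variance 1 − p², and the adjusted or constrained effect has (1 − p²) − (r − p²)²/(1 − p²). For example, at r = 0.5 and p = 0.2: 0.96 − 0.46²/0.96 = 0.740. The change contrast is untouched by PHQ-9, because a covariate that is constant over time cancels from it.

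| Relative variance | r = 0.3 | r = 0.5 | r = 0.7 |
|---|---|---|---|
| 3-month difference, p = 0 / 0.2 / 0.4 | 1 / 0.960 / 0.840 | same | same |
| Change from baseline | 1.40 | 1.00 | 0.60 |
| Adjusted or constrained, p = 0 | 0.910 | 0.750 | 0.510 |
| Adjusted or constrained, p = 0.2 | 0.890 | 0.740 | 0.506 |
| Adjusted or constrained, p = 0.4 | 0.817 | 0.702 | 0.493 |

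**4. Power at d = 0.42** (noncentral t, 178 df, standardised effect 0.42/√variance):

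| Test | r = 0.3 | r = 0.5 | r = 0.7 |
|---|---|---|---|
| 3-month difference, p = 0 / 0.2 / 0.4 | 80.0 / 81.6 / 86.4 | same | same |
| Change from baseline | 65.8 | 80.0 | 95.1 |
| Adjusted or constrained, p = 0 | 83.6 | 89.9 | 97.5 |
| Adjusted or constrained, p = 0.2 | 84.4 | 90.3 | 97.6 |
| Adjusted or constrained, p = 0.4 | 87.3 | 91.7 | 97.9 |

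**5. Size against the 3-month difference with PHQ-9 already in the model.** The further variance reduction is 3–7%, 16–23% and 41–47% at r = 0.3, 0.5 and 0.7. In participants, 180 × (variance ratio) gives 194, 234 and 341 at p = 0.2 (for example 180 × 0.960/0.740 ≈ 234) and 185, 215 and 307 at p = 0.4.

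**6. If time is linear over 0, 3 and 6 months.** Ignoring PHQ-9, the variance of slope × 3 months is 0.35, 0.25 and 0.15 with free baselines, against 0.211, 0.182 and 0.126 with equal baselines (ratios 1.66, 1.38 and 1.19). With PHQ-9 the ratios are 1.71–1.94, 1.40–1.49 and 1.20–1.23. Separately, if the full effect of 0.42 is present at month 3 and holds to month 6, slope × 3 months estimates 0.21 (free) or 0.22–0.24 (constrained). The baseline constraint does not cure that; categorical time does.

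**The case against.** The strongest reply is that nothing stated is wrong. The analysis is valid under randomisation, the power figures reproduce, and on the 3-month-difference reading the planned test has at least 80% power at every assumed r, rising to 82–86% once PHQ-9 is credited. That stands, and it is why this is an efficiency improvement and not an error.

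The size also rests on correlations that the protocol does not report. The two main readings move in opposite directions: the 3-month difference loses most at high r, the change contrast at low r. At r = 0.3 the gain over the 3-month difference is negligible, and at r = 0.7 the gain over the change contrast is only 2–3 points. So no single loss can be attributed to the plan. Even so, the adjusted or constrained analysis is the more precise at every value examined.

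The protocol does not say that PIH is collected at baseline; this is inferred from its reference to baseline measures. If it is not collected, there is no precision to recover by wording alone. This condition stands and comes first in the fix.

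Finally, no passage says time is linear, and the understated 3-month effect under a linear slope comes from the time coding, not from the missing baseline adjustment. That is fair: the linear reading is only a possibility that the text leaves open, and a reason to state the coding.

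**Conclusion.** The concern holds. As written, the primary model makes no use of baseline PIH as a covariate or through a common baseline mean, and on each reading of the unspecified 3-month test it is less precise than an analysis that does.

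At r = 0.5, with PHQ-9 credited, the loss is 5–9 points of power against the 3-month difference and 10–12 points against the change contrast (80% against 90–92%). Power falls below the stated 80% only if the change contrast is the test and r is under 0.5.

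These sizes assume complete data, equal correlation between visits, a baseline PHQ-9 and the stated ranges of r and p. The direction does not depend on where r falls in its range. The trial is not invalidated and no stated figure needs correcting; the change is worth making before the outcome data are analysed. Confidence in the size is moderate, because r is unknown and baseline collection of PIH is inferred.

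**What to change.** First confirm that PIH is in the baseline survey. Then replace the model description with one of two specifications; either is acceptable:

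- (i) Baseline, month 3 and month 6 PIH as outcome rows, time categorical, arm means constrained equal at baseline, so that treatment terms enter at months 3 and 6 only; or
- (ii) Month 3 and month 6 PIH as outcomes, time categorical, with baseline PIH and its interaction with time as covariates.

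In both, name the treatment contrast at month 3 as the single primary test, in place of the general reference to treatment as the effect of interest. Keep the planned covariates, and state that the PHQ-9 total score is the baseline value.

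The cost is analysis-plan wording only, provided PIH is already collected at baseline. Option (i) adds no covariate. Option (ii) uses about one degree of freedom per added term and includes only participants with at least one follow-up score. The sample size and power statement can stay as they are; they then describe a conservative, unadjusted comparison.
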